5.4.3.2. Vital Signs

5.4.3.2.1. Definition of Vital Signs variables

5.4.3.2.1.1. Blood Pressure

Per protocol, blood pressure measurements, including systolic (SBP) and diastolic (DBP) blood pressure will be performed at all scheduled study visits, both during the core and the extension study.

Data is stored along with nominal visit and time point labels that will be used for the analysis. Data from both studies (core and extension) will be pooled for the analysis.

At all assessments (except the hourly post-dose assessments after first dose on Day 1 at reinitiation), blood pressure will be measured twice (i.e., two SBP measurements and two DBP measurements) and recorded in the eCRF. The average of the two values will be calculated on the eCRF and recorded as "Mean SBP" and "Mean DBP". For all data analysis, baselines, and for flagging of high or low values, these mean values will be used. If only one measurement is available, this is used for all further derivations and summary statistics.

Extension / core baseline is flagged and absolute and percent changes from extension/core baseline are calculated for each post-baseline value. In the same manner, pre-dose values are flagged and

absolute and percent change from pre-dose are calculated for the hourly post-dose assessments after first dose on extension study Day 1 at re-initiation.

For by-visit and by-hour tables presenting summary statistics of quantitative vital signs results, the latest (by date/time) transmitted measurement per nominal subject-visit / time point is used in case of multiple data available at that visit or visit / time point.

Assessments meeting the following conditions for notable abnormalities are flagged in the ADaM dataset:

- SBP \leq 90 mmHg or \geq 20 mmHg decrease from baseline;
- SBP \leq 90 mmHg;
- \geq 20 mmHg decrease from baseline in SBP;
- SBP \geq 160 mmHg or \geq 20 mmHg increase from baseline;
- SBP \geq 160 mmHg;
- SBP ≥140 mmHg;
- \geq 20 mmHg increase from baseline SBP;
- DBP \leq 50 mmHg or \geq 15 mmHg decrease from baseline;
- DBP \leq 50 mmHg;
- \geq 15 mmHg decrease from baseline in DBP;
- DBP \geq 100 mmHg or \geq 15 mmHg increase from baseline;
- DBP \geq 100 mmHg;
- DBP \geq 90 mmHg;
- ≥15 mmHg increase from baseline in DBP.

The above flags are derived for the Extension Analysis Period using extension baseline as a reference, and additionally for the Combined Analysis Period using the core baseline value as a reference.

For all hourly post-dose assessments after first dose on extension study Day 1 at re-initiations during the extension, flags are set for the following conditions:

- SBP \leq 90 mmHg or \geq 20 mmHg decrease from pre-dose;
- \geq 20 mmHg decrease from pre-dose in SBP;
- DBP \leq 50 mmHg or \geq 15 mmHg decrease from pre-dose;
- \geq 15 mmHg decrease from pre-dose in DBP.

For details of the vital signs abnormality flags derived during the core study, see the core SAP [D-19.178]. These variables are used as derived in the core study, and are not re-derived for the extension analysis.

5.4.3.2.1.2. Weight

Weight is collected in the eCRF of the core study at Screening, Visit 10 (Week 60), EOT Visit (Week 108), and at unscheduled visits; and in the eCRF of the extension study at Visits 7, 11, 15, 19, and EOT (Weeks 48, 96, 144, 192, and 240), and at unscheduled visits.

Data is stored along with nominal visit and time point labels that will be used for the analysis. Absolute and percent change from core/extension baseline is calculated for each post-baseline weight (kg) value.

CONFIDENTIAL – FOIA Exemptions Apply in U.S.

5.4.3.2.1.3. Body Temperature

Body temperature is collected at all visits in the Body Temperature eCRF as 'normal' or 'abnormal' both for the core and the extension studies.

No definitions and derivations (other than treatment day of assessment) are necessary.

5.4.3.2.1.4. Pulse rate

Pulse rate is collected as 'normal' or 'abnormal' at unscheduled visits in the Pulse Rate eCRF of the core and extension studies, and additionally at visits where no 12-lead ECG is performed during the extension study (as indicated in Protocol Table 12 and Table 13).

No definitions and derivations (other than treatment day of assessment) are necessary.

5.4.3.2.2. Analysis of Vital Signs

The following outputs will be produced for blood pressure (SBP and DBP) and body weight, both for the Combined Analysis Period, by core study treatment, using SAF (the summaries marked with § will include only the subjects who were initially treated with ponesimod 20 mg in the core study), and for the Extension Analysis Period, by core study treatment and overall using the EXTS:

- Summary of absolute values for blood pressure parameters and body weight: descriptive statistics by visit;
- Summary of absolute and absolute change from baseline values for blood pressure parameters and body weight: descriptive statistics by visit; mean changes from baseline in blood pressure are also presented graphically with their standard error over time (plots starting with zero change at baseline);
- Number and percentage of subjects with any treatment-emergent blood pressure result meeting the criteria defined in Section 5.4.3.2.1 Percentages are based on the number of subjects with at least one treatment-emergent result available for the corresponding parameter.§

The following outputs will be produced for blood pressure (SBP and DBP), for the Extension Analysis Period only, by core study treatment and overall using the EXTS:

- Summary of pre- and post-dose values for vital signs parameters on Day 1 of first reinitiation: descriptive statistics time point. Note: data from re-initiations beyond the first are listed only; Strictly speaking the Day 1 of extension study is also counted as "Day 1 of first re-initiation" as subjects had experienced study treatment interruption between end of core study and start of extension study. Nevertheless in this context the "Day 1 of first re-initiation" applies for re-initiation after a study drug interruption during extension period.
- Summary of absolute and absolute change from pre-dose to post-dose values for vital signs parameters on Day 1 of first re-initiation: descriptive statistics by time point. Note: data from re-initiations beyond the first are listed only;
- Number and percentage of subjects with any post-dose blood pressure result meeting the criteria defined in Section 5.4.3.2.1 on Day 1 of (any) re-initiation. Percentages are based on the number of subjects with at least one post-dose blood pressure result available for the corresponding parameter.

Unscheduled visits are not presented in summary tables by visit. Unscheduled assessments that meet the pre-defined high/low criteria will be flagged and included in the corresponding incidence tables.

The outputs summarizing high and low blood pressure will only use treatment-emergent data.

All notable abnormality in blood pressure (as specified above) are listed by core study treatment group and visit.

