5.1.6. Definition of treatment-emergent

A safety assessment (ECG, vital signs, laboratory, etc.) is considered treatment-emergent relative to the Analysis Period, and a safety event (AE, serious adverse event [SAE], Death, etc.) is considered treatment-emergent relative to the Analysis Period, if the assessment date is on or after the study treatment start date in the Analysis Period and prior to or on the study treatment end date + 15 days (inclusive). In case of planned pregnancy interruption, a safety assessment is considered treatment emergent relative to the Analysis Period if one of the following conditions is met:

- the assessment date is on or after the study treatment start date in the Analysis Period and prior to or on the last study drug intake date prior to pregnancy interruption + 15 days (inclusive)
- the assessment date is on or after the re-initiation date of study treatment after planned pregnancy and prior to or on the End of Treatment (EOT) date + 15 days (inclusive).

In case of multiple planned pregnancies interruptions, the above definition will be adapted, that any assessment in the following interval is not considered as treatment emergent: date between the last study drug intake date prior to each pregnancy interruption + 15 days (inclusive) and the reinitiation date of study treatment after each planned pregnancy (excluded).

If both the assessment date/time and the date/time of study treatment start (or of re initiation after planned pregnancy) are available, only events with date/time on or after the date/time of study treatment start (or of re initiation after planned pregnancy) are considered to be treatment emergent. In case of (partially) missing assessment dates/times, or for assessments on treatment Day 1 with reported assessment time contradicting the time point label, the nominal visit and time point labels will be used to determine whether an assessment is considered as treatment-emergent or not. For example, a blood pressure measurement with an assessment date on Day 1 but a missing assessment time or an assessment time after the time of first study drug intake, will not be considered treatment emergent if reported under the time point "Pre-dose" in the eCRF, however it will be considered treatment-emergent if reported as "2 hours post-dose" in the eCRF.

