5.4.3.1.2. Analysis of Laboratory Tests

The following tables will be produced for laboratory tests, both for the Combined Analysis Period, by core study treatment, using SAF (the summaries marked with § will include only the subjects who were initially treated with ponesimod 20 mg in the core study), and for the Extension Analysis Period, by core study treatment and overall, using the EXTS.

- Summary of absolute and absolute change from baseline values for laboratory tests (hematology, blood chemistry [excluding liver tests], liver tests): descriptive statistics by visit;
- Summary of percent change from baseline values for lymphocyte counts: descriptive statistics by visit;

CONFIDENTIAL – FOIA Exemptions Apply in U.S.

- Incidence of marked laboratory abnormalities (LL, LLL, HH, HHH) as defined in Section 6.10: frequency counts and percentages, where percentages are based on the number of subjects with at least one post-baseline value in the Analysis Period (i.e., number of subjects at risk);§
- Incidence of special laboratory abnormalities for ALT, AST, Bilirubin, and ALP: frequency counts and percentages, where percentages are based on the number of subjects with at least one post-baseline value (i.e., number of subjects at risk);§
- Incidence of marked treatment-emergent laboratory abnormalities for lymphocyte counts: frequency counts and percentages, where percentages are based on the number of subjects with at least one post-baseline value (i.e., number of subjects at risk)§.
- A plot to evaluate Drug-Induced Serious Hepatotoxicity (eDISH plot) based on the highest observed treatment-emergent ALT and total bilirubin values will be provided for safety analysis set during combined period, as well as for extension period by treatment group. Individual subject's values expressed as × ULN are plotted on a log-log scatter plot (ALT on the horizontal axis, total bilirubin on the vertical axis); reference lines are drawn at Hy's law thresholds, i.e., at 3 × ULN for ALT and at 2 × ULN for total bilirubin.

For abnormalities, the worst case in each direction is considered and summarized in all applicable categories, i.e., a subject counted in LLL is also counted in LL for a given parameter; also, a subject maybe counted in both the high and the low category for a given parameter.

[figure not shown]
Unscheduled assessments that meet the pre-defined high/low criteria will be flagged and may be included in the corresponding incidence tables.

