- Incidence of clinically relevant morphological ECG findings on Day 1 of (any) re-initiation by abnormality and group term, overall and by time point: frequency counts and percentages.

Only newly occurring treatment-emergent abnormalities and findings are reported, i.e. if a subject has a particular event/finding prior to first treatment in the Analysis Period, and the same event/finding occurs again during the Analysis Period, it will not be reported in the summary table. "Pre-existing" findings will be only flagged in datasets and reported in listing. Unscheduled visits are not presented in summary tables by visit. Unscheduled assessments that meet the pre-defined high/low criteria will be flagged and may be included in the corresponding incidence tables.

All ECG notable abnormality data as specified above will be included in listings.

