5.4.3.4.2. Analysis of Spirometry and DLCO

Spirometry:

The following outputs will be produced for PFTs, both for the Combined Analysis Period, using SAF, and for the Extension Analysis Period, using the EXTS:

- Summary of absolute values for PFT parameters (FEV₁, FVC, FEV₁/FVC ratio, %PRED FEV₁, %PRED FVC): descriptive statistics by visit;
- Summary of absolute change from baseline values for PFT parameters (FEV₁, FVC, FEV₁/FVC ratio, %PRED FEV₁, %PRED FVC): descriptive statistics by visit;
- Summary of percent change from baseline values for PFT parameters (FEV₁, FVC, FEV₁/FVC ratio, %PRED FEV₁, %PRED FVC): descriptive statistics by visit;
- Summary of absolute change from baseline values for PFT parameters (FEV1, FVC, FEV₁/FVC ratio, %PRED FEV₁, %PRED FVC): mean plot with core study treatment group color-coded (plot starting with zero change at baseline).
- Summary of percent change from baseline values for PFT parameters (FEV₁, FVC, FEV₁/FVC ratio, %PRED FEV₁, %PRED FVC): mean plot with core study treatment group color-coded (plot starting with zero change at baseline).

In addition, the following outputs will be produced both for the Combined Analysis Period, using the SAF and only for subjects who received ponesimod 20 mg in the core study, and for the Extension Analysis Period, using the EXTS:

• Incidence of treatment-emergent spirometry outliers [as defined in Section 5.4.3.4.1]: frequency counts, percentages, where percentages are based on the number of subjects with at least one treatment-emergent result available for the corresponding parameter.

Unscheduled visits are not presented in summary tables by visit. Unscheduled assessments that meet the pre-defined high/low criteria will be flagged and may be included in the corresponding incidence tables.

All notable abnormality in spirometry results (best effort results from core study and all results from extension study) will be listed by study treatment group and visit.

In addition, to understand the change in PFT parameters (FEV1, FVC, FEV1/FVC ratio, %PRED FEV1, %PRED FVC) after EOT, the following analyses will be done for subjects who continue any DMT (see section 6.5.1.4 for DMT list) after EOT date versus subjects who have no DMT after EOT date (irrespective of the original treatment group):

- Absolute values of PFT parameters over the following visits: Core baseline, Extension Baseline, Extension EOT, Extension EOS and the change from Core baseline using EXTS.

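### Fixed cut-off blood pressure, laboratory and FEV1/FVC abnormalities count as treatment-emergent even when the same criterion was met at baseline; the counts should be split by baseline status

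*SAP*

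**What the plan says.** Section 5.1.6 treats a safety assessment as treatment-emergent if the "assessment date is on or after the study treatment start date in the Analysis Period" and no later than 15 days after treatment end, with gaps for planned pregnancy. Baseline status plays no part.

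Three sections apply this window to cut-offs:

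- **Blood pressure (5.4.3.2.1, 5.4.3.2.2).** The stand-alone limits are SBP ≤ 90, ≥ 140 and ≥ 160 and DBP ≤ 50, ≥ 90 and ≥ 100 mmHg, listed beside change-from-baseline criteria. The table gives the "Number and percentage of subjects with any treatment-emergent blood pressure result meeting the criteria defined in Section 5.4.3.2.1". Its denominator takes in everyone who has a value of that parameter in the on-treatment window, whatever the baseline was.
- **Laboratory (5.4.3.1.2, Table 11).** Marked abnormalities, liver-test multiples of ULN and lymphocyte classes are tabulated. For marked abnormalities, "percentages are based on the number of subjects with at least one post-baseline value in the Analysis Period (i.e., number of subjects at risk"). Section 5.4.2.3 restricts tables to treatment-emergent data unless stated otherwise.
- **Spirometry (5.4.3.4.1, 5.4.3.4.2).** The table is "Incidence of treatment-emergent spirometry outliers", and the flags include FEV1/FVC < 70%.

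The ECG section (5.4.3.3.2) goes further: "Only newly occurring treatment-emergent abnormalities and findings are reported". Findings present before first treatment in the period go to datasets and listings only.

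**The concern.** Treatment-emergent notable blood pressure and laboratory abnormalities are named safety endpoints in Table 2. For fixed cut-offs, the planned percentage mixes two groups: subjects who crossed the limit on treatment, and subjects who were already beyond it and stayed there. No planned blood pressure, laboratory or spirometry table separates them. The only baseline-to-worst shift table in the SAP is for the eC-SSRS (5.4.3.9.2).

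The design gives little help in separating them. The Combined Analysis Period versions of these incidence tables show only subjects initially treated with ponesimod, and everyone in the extension takes ponesimod, so there is no concurrent comparator to show the background. In the Extension Analysis Period subjects arrive after 108 weeks of active treatment. Someone who enters with raised ALT or low lymphocytes, and meets the cut-off again, is in the count.

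**Working it through.** The SAP states no figure for these rates, so there is nothing to reproduce. Three checks were made.

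**1. The rules applied to values that do not worsen**

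| Parameter | Baseline | On treatment | Result under the SAP |
|---|---|---|---|
| SBP (mmHg) | 162 | 160 | counted at ≥ 160 and ≥ 140 |
| SBP (mmHg) | 145 | 142 | counted at ≥ 140 |
| SBP (mmHg) | 88 | 90 | counted at ≤ 90 |
| Hemoglobin (g/L) | 98 | 98 | counted as LL |
| Creatinine | above 1.5 ULN | unchanged | counted as HH |
| FEV1/FVC | 0.68 | 0.68 | counted at < 70% |
| Hemoglobin, high | more than 20 g/L above ULN | unchanged | not counted as HH |

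The last row is protected because Table 11 switches hemoglobin HH/HHH to an increase from baseline when baseline exceeds ULN. Creatinine also has a baseline clause, but it is joined by *or* and so does not protect. Change-from-baseline criteria (SBP and DBP change, percent change in FEV1 and FVC, change in percent predicted) do not have this problem.

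**2. General size**

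Let b be the share beyond the cut-off at baseline, r the share of those beyond it again on treatment, and i the new-onset share among the rest. None of the three is in the SAP.

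Reported share = b·r + (1 − b)·i

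Excess over new onset = b·r + (1 − b)·i − i = b·(r − i)

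With i = 5%, on the 877 enrolled subjects (Section 3):

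| b | r | Reported | New onset | Carried-over subjects (877·b·r) |
|---|---|---|---|---|
| 2% | 0.6 | 6.1% | 5.0% | 11 |
| 2% | 0.9 | 6.7% | 5.0% | 16 |
| 5% | 0.6 | 7.8% | 5.0% | 26 |
| 5% | 0.9 | 9.2% | 5.0% | 39 |
| 10% | 0.6 | 10.5% | 5.0% | 53 |
| 10% | 0.9 | 13.5% | 5.0% | 79 |
| 15% | 0.6 | 13.2% | 5.0% | 79 |
| 15% | 0.9 | 17.8% | 5.0% | 118 |

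**3. Systolic blood pressure with no drug effect**

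This is a simulation with assumed inputs: mean SBP 120 mmHg, between-subject SD 11, visit-to-visit SD 6, 8 or 10, and 24 on-treatment visits. A subject is flagged if any visit meets the cut-off.

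| Cut-off | Visit SD | Beyond at baseline (b) | Flagged, SAP rule | Flagged among those not beyond at baseline (i) |
|---|---|---|---|---|
| ≥ 140 | 6 | 5.4% | 23% | 19% |
| ≥ 140 | 8 | 7.1% | 35% | 31% |
| ≥ 140 | 10 | 8.9% | 48% | 44% |
| ≥ 160 | 6 | 0.07% | 0.7% | 0.6% |
| ≥ 160 | 8 | 0.16% | 2.0% | 1.8% |
| ≥ 160 | 10 | 0.35% | 4.7% | 4.5% |

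For SBP ≥ 140, 94 to 95% of subjects beyond the limit at baseline are flagged again. The formula then gives an excess of 0.054 × (0.952 − 0.190) = 4.1 points at SD 6, 0.071 × (0.939 − 0.307) = 4.5 points at SD 8 and 0.089 × (0.936 − 0.436) = 4.5 points at SD 10. These carried-over subjects are 17 to 22% of all flagged subjects, so most flagged subjects were below 140 at baseline. For SBP ≥ 160 the excess is at most about 0.2 points.

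**The case against.** The strongest reply is that treatment-emergent is defined openly as an on-treatment window, and that new is a separate label used only for ECG findings. The study is descriptive and has no hypotheses. Read this way, the tables correctly give the share of subjects with an on-treatment value beyond a limit. That stands. A reader might infer that the percentages are offered as evidence that ponesimod causes the abnormalities. The SAP makes no such claim, and no single-arm table could support one.

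A reader might also infer that the denominator is wrong throughout and that subjects abnormal at baseline should be removed from the tables. The documents do not support that, for two reasons. The ECG tables use the same at-risk denominator, so the SAP's own stricter rule concerns the numerator only. Removal could also hide drug effects. Extension baseline is the last value from the core EOT visit up to first extension dose (5.1.3.1), and the core follow-up visits fall 14 to 37 days after the last core dose (1.2.1). In ponesimod/ponesimod subjects, low lymphocytes or raised ALT at that point may be ponesimod's own effect. Section 5.5.3 also classifies the lowest lymphocyte count, which describes the nadir rather than new onset.

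Other limits stand as well. FEV1/FVC < 70% is not a Table 2 endpoint; the treatment-emergent pulmonary endpoints there are decreases from baseline. Blood pressure change flags, by-visit change summaries and listings of blood pressure abnormalities and lymphocyte counts give part of the missing information. Core-period blood pressure and spirometry flags are taken from a core SAP that is not shown, although the incidence tables here add no new-onset condition. How often change flags fire at any single visit is a different question and lends this point no support.

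What the reply does not answer is why ECG tables separate new from pre-existing abnormalities while the blood pressure and laboratory endpoint tables do not.

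**Conclusion.** The point holds for stand-alone fixed cut-offs: the six blood pressure limits, the ALT, AST and bilirubin multiples of ULN, the marked laboratory abnormalities in Table 11 other than hemoglobin HH/HHH, the lymphocyte classes and, as a secondary flag, FEV1/FVC < 70%. For these, an unchanged pre-existing abnormality counts as treatment-emergent, and no planned table shows how many of the counted subjects are of that kind. This is inconsistent with the SAP's own ECG rule.

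The size cannot be taken from the SAP. It depends on how common the abnormality is at baseline and how persistent it is. Under the assumed blood pressure inputs it is modest for a common cut-off (about 4 to 5 points for SBP ≥ 140) and negligible for a rare one (SBP ≥ 160). It is a reporting gap in safety tables that should be closed. The on-treatment percentages themselves are not invalid.

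**What to change.** In 5.4.3.1.2, 5.4.3.2.2 and 5.4.3.4.2, for each fixed cut-off:

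- Keep the existing all-subjects on-treatment row, and keep the lymphocyte nadir table.
- Split that row by whether the baseline of that Analysis Period met the same criterion: new or worsened grade versus pre-existing. Give the new-onset row a denominator of subjects with a post-baseline value who did not meet the criterion at baseline. A baseline-to-worst shift table would serve equally well.
- Label only the new or worsened row as newly occurring.

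The cost is SAP wording and one extra condition in existing programs, since core and extension baselines are already flagged for these parameters. No data collection changes. Because the all-subjects row stays, no information on persistent or carried-over abnormalities is lost.
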